## A.10. Confidentiality of the data

A.10.1. Describe procedures for maintaining confidentiality of the data you will collect or will receive (e.g., coding, anonymous responses, use of pseudonyms, etc.).

Research data will be identified only by study identification numbers (IDs). These study IDs will be used to maintain relationships in the data between various tables. All consent forms and any paper data collection instruments will be stored in a locked cabinet in a secure location. The list identifying subjects with their contact information will be kept separate from the scientific study data.

Database Security. The database will be created within centralized files and maintained on University approved; password protected, encrypted, shared research drives in the orthopaedic surgery department and viewed only on approved devices by approved study personnel.

PHI Security. Procedures to maintain privacy and confidentiality will be followed rigorously. For each subject, identifying information and protected health information (PHI; e.g., demographic information, medical history, laboratory results, insurance information) will be collected along with scientific study data (e.g., treatment group assignment, medical chart data, responses to treatment). Each research subject will be assigned a study identification number (ID). The scientific study data will be stored in a digital file that does not include patient identifiers or PHI. A separate data file will contain identifiers and PHI. A master file linking patient identifiers to the study data will be kept by the principal investigator. The database will be password protected and will be stored on servers housed in a secure location.

Confidentiality. Research data will be identified only by study identification numbers (IDs). These study IDs will be used to maintain relationships in the data between various tables. All consent forms and any paper data collection instruments will be stored in a locked cabinet in a secure location. The list identifying subjects with their contact information will be kept separate from the scientific study data.

A.10.2. Describe how data will be transmitted among research team (i.e., personnel listed on this application).

Digital transmission of the data will be encrypted. Transportation of the data will use secure media.

A.10.3. Are you collecting sensitive information such as sexual behavior, HIV status, recreational drug use, illegal behaviors, child/physical abuse, immigration status, etc?

No

A.10.4. Do you plan to obtain a federal Certificate of Confidentiality for this study?

No

A.10.5. If relevant, discuss the potential for deductive disclosure (i.e., directly identifying subjects from a combination of indirect IDs).

We will minimize the risk of unauthorized persons using the database to figure out a subject's identity and responses.

(1) The database will comprise two separate files: a TRACKING FILE (containing sensitive patient identifiers such as name, birthdate, date and time of admission to the ER, and Subject\_ID) and a de-identified RESEARCH FILE containing non-sensitive data such as Subject\_ID, age, treatment assignment, ASEPSIS data, etc. Both database files contain Study\_ID. This allows the two sets of information to be linked together if necessary, but prevents linkage as long as the two files are kept safely separated.

(2) The database will be secured on encrypted storage media to guard against hacking or other unauthorized access. Paper forms will be stored in locked locations.

(3) Data will be retrieved from the RESEARCH FILE and distributed to specific personnel (e.g., the P.I., or co-investigators) for purposes of statistical computations for preparation of publications. Storage, retrieval and distribution will be carefully and securely controlled. Digital transmission of the data will be encrypted. Transportation of the data will use secure media.

A.10.6. Will any of the groupings or subgroupings used in analysis be small enough to allow individuals to be identified?

No

## A.11. Data sharing and transmission

A.11.1. Check all of the following who will receive **identifiable data** (contains any of the 18 identifiers listed above) outside the immediate research team (i.e., not listed as personnel on this application)? \*

- No one
- Coordinating Center
- Statisticians
- Consultants
- Other researchers
- Registries
- Sponsors
- External labs for additional testing
- Journals
- Publicly available dataset
- Other

A.11.2. For any recipients checked above, explain the confidentiality measures to be taken

No Answer Provided

## A.12. Post-study disposition of identifiable data or human biological materials

A.12.1. Describe your plans for disposition of data or human biological specimens that are identifiable in any way (directly or via indirect codes) once the study has ended. If you plan to destroy linkage codes or identifiers, describe how and when this will be done.

Following publication Identifiable information will be deleted from UNC Secure servers and physical data will be shredded. Data with non identifiable data (e.g. patient\_1, patient\_@, etc...) and study data will be kept on a secure drive for further research needs and planning of future studies.

## Part B. Direct Interaction

### B.1. Methods of recruiting

B.1.1. Check all the following means/methods of subject recruitment to be used:\*

- In person
- Participant pools
- Presentation to classes or other groups
- Letters
- Flyers
- Radio, TV recruitment ads
- Newspaper recruitment ads
- Website recruitment ads
- Telephone script
- Email or listserv announcements
- Follow up to initial contact (e.g., email, script, letter)
- Other

B.1.2. Describe how subjects will be identified

Patients will be patients previously scheduled for primary total hip arthroplasty in [name] clinic.

B.1.3. Describe how and where subjects will be recruited and address the likelihood that you will have access to the projected number of subjects identified in A.2.

All patients will be previously scheduled for primary total hip arthroplasty in [name] clinic. [name] performs approximately 10 primary total hip arthroplasties per month.

B.1.4. Describe how you will protect the privacy of potential subjects during recruitment

All patient data will remain on secured servers.

B.1.5. Describe how subjects will be contacted, if not addressed above

Subjects will be previously scheduled for clinic visits in preparation of total hip arthroplasty surgery.

B.1.6. Describe who will do the recruiting

Recruiting will be performed by the resident surgeon during clinic visits.

B.1.7. Describe efforts to ensure equal access to participation among women and minorities

All patients regardless of demographics will be recruited. No difference in recruiting efforts will be made.

## B.2. Protected Health Information (PHI)

*Protected Health Information (PHI) is any identifiable information about the subject's health that relates to their participation in this research and is obtained from sources other than the subject, such as medical records, health care providers, insurance plans, etc. [more](#)*

B.2.1. Are you requesting a limited waiver of HIPAA authorization?

If you need to access Protected Health Information (PHI) to identify potential subjects who will then be contacted, you will need a [limited waiver of HIPAA authorization \(see SOP 29.3\)](#). This does not apply to situations where you will never contact subjects directly (e.g., retrospective chart review), in which case you should request a full waiver under section D.

Yes

Will you access the records of 50 or more patients under this limited waiver?

Yes

Please provide a response to each of the following questions:

Under this limited waiver, you are allowed to access and use only the minimum amount of PHI necessary to review eligibility criteria and contact potential subjects. Describe the information you are planning to collect for this purpose

Name, Age, Medical comorbidites, surgical plan, surgical history

Describe how confidentiality/privacy will be protected prior to ascertaining the patient's willingness to participate

No patient information will be recorded prior to participation, prior to recruitment the patient's will be identified before clinic and highlighted for recruitment.

Describe when and how you will destroy the contact information if an individual declines participation

Patient's that decline to participate will have no information previously recorded and all schedules with identification for study enrollment will be shredded securely.

B.2.2. Will you need ongoing access to PHI (e.g., medical records) to conduct the study, beyond the identification of potential subjects as addressed above? In this case you will need to obtain a signed HIPAA Authorization from each subject.

Yes

*In order to access patient records you are required to provide a copy of the IRB approval letter and copies of signed HIPAA authorization forms for each patient whose record you will access, to Healthcare Information Management (HIM).*

## B.3. Subject Contact, Duration and Privacy

B.3.1. Number of contacts per subject

6

B.3.2. Duration of each contact. If multiple contacts, provide the range or average time for each contact.

Contact will be limited to outpatient clinic visits that will involve the recruitment and wound checks. No more than 10 minutes of each visit will be devoted to research other than recruitment.

B.3.3. Total duration of individual subject's participation, including follow up evaluation, if applicable

8 weeks

B.3.4. Where are you studying subjects or obtaining their data?

Healthcare setting

Please check all that apply:

- UNC Medical Center (N.C. Memorial Hospital, N.C. Children's Hospital, N.C. Womens' Hospital, N.C. Cancer Hospital, N.C. Neurosciences Hospital, Ambulatory Care Center (ACC))
- Rex Healthcare
- Chatham Hospital
- Johnston Memorial
- Pardee Hospital
- High Point Regional Health
- Caldwell Memorial Hospital
- UNC Physician Network - affiliated site(s)
- Other

B.3.5. Provide more information about the location(s) where research will be conducted (e.g., if UNC Medical Center is checked in #4 above and study visits will be conducted in the CTRC, enter "CTRC" here.)

All subjects will be studied at the UNC Orthopaedic clinic.

[name]

[name]

B.3.6. Describe procedures that will ensure privacy of the subjects in this study. Examples include the setting for interviews, phone conversations, or physical examinations; communication methods or mailed materials (e.g., mailings should not indicate disease status or focus of study on the envelope)

All patient contact will occur in outpatient clinic rooms that will only contain the individual involved in the research study.

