### ASEPSIS Scoring System

Characteristic	Percent of Wound Affected					
	0	<20	20-39	40-59	60-79	>80
Serous Exudate	0	1	2	3	4	5
Erythema	0	1	2	3	4	5
Purulent Exudate	0	2	4	6	8	10
Separation of Deep Tissue	0	2	4	6	8	10

Additional Points for: Antibiotic Treatment- 10 Local Debridement- 5 OR Debridement- 10 Isolation of Bacteria- 10 Hospitalization >14 days- 10

The scoring system is designed to translate the appearance of the wound with the clinical appearance. Stricter methods of evaluating wounds (such as evaluating for pus) can miss lesser degrees of infection. This score helps to overcome the challenge of a small incidence of grossly infected wounds by identifying the skin changes associated with infection. Wilson et al. identified an ASPESIS score >20 as being more sensitive and as specific as the presence of pus as an indicator of changes in management resulting from infection [24]. The scoring method has also been shown to be both repeatable (intraobserver reliability of 0.96 and coefficient of repeatability of 4.1) and validated against the CDC criteria in general surgery procedures.[22,25]

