### A.4. Study design, methods and procedures

*Your response to the next question will help determine what further questions you will be asked in the following sections.*

A.4.1. Will you be using any **methods or procedures commonly used in biomedical or clinical research** (this would include but not be limited to drawing blood, performing lab tests or biological monitoring, conducting physical exams, administering drugs, or conducting a clinical trial)?

Yes

A.4.2. Describe the study design. List and describe study procedures, including a sequential description of what subjects will be asked to do, when relevant.

Patients will undergo primary total hip arthroplasty with identical preoperative and intraoperative care. The patients will then be divided into two groups depending on their randomization. All postoperative care will remain the same other than the choice of dressing placed postoperatively. They will remain in the hospital for 2-3 days(standard of care). On Post op day two they will receive a dressing change regardless of their regimen(standard of care). Patients will be discharged home or to a skilled nursing facility with instructions regarding wound care in both regimens. They will receive assistance through home health or through their nursing facility in case of dressing issues although there will be no intended dressing change or other alteration of the dressing until their next followup. Instructions for the study will be included in the discharge instructions and

include a phone number for questions, these instructions are provided on another attachment. The patients will return to clinic on Post op day seven. They will have their wound evaluated and the dressing changed with their wound evaluated for ASEPSIS (the details of the scoring system and references are provided in the background). They will return on post op day 14 and again have their wound evaluated. Their staples will also be removed. They will be monitored until their 6 week visit for any complications.

Standard Regimen.

Post Op Dressing	Staples over surgical incision, Adaptic® dressing, Abdominal Dressing pad, Tape
POD2	All dressings removed, staples remain in place, Island dressing placed
1 Week Post Op	Island dressing removed and new sterile island dressing placed *Wound evaluated
2 Weeks Post Op	Island dressing removed and staples removed, no dressing placed *Wound evaluated

Experimental Regimen.

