## A.7. Data and safety monitoring

A.7.1. When appropriate, describe the plan for monitoring the data to ensure the safety of participants.

These plans could range from the investigator monitoring subject data for any safety concerns to a sponsor-based data and safety monitoring board or committee (DSMB, DSMC, DMC), depending on the study. For studies that do not raise obvious safety concerns, you may still describe your plans for monitoring the study as it progresses.

The investigator and the attending's nurse will be monitoring the patients continuously as the study progresses. Patients will be in the hospital for 2-3 days following surgery and will return to clinic around post op day 7 and 14. During that time they will be maintained on a monitoring list to identify any readmissions and to ensure appropriate followup. They will have a number for any issues and these will be provided to the research team to ensure appropriate care.

A.7.2. If not already addressed above, describe the plans for aggregate review of unanticipated problems (including but not limited to adverse events) across all sites, in order to monitor subject safety.

Any adverse event/unanticipated problem will result in disclosure to the IRB and proper response by the PI and investigator team.

A.7.3. What are the criteria that will be used to withdraw an INDIVIDUAL SUBJECT from this study or halt the research intervention (e.g., abnormal lab tests, allergic reactions, failure or inability to comply with study procedures, etc.)?

Patients that sustain allergic reactions, complications necessitating further treatment, or other unanticipated adverse event will be withdrawn from the study and proper care initiated.

A.7.4. Are there criteria that will be used to stop the ENTIRE STUDY prematurely (e.g., safety, efficacy, unexpected adverse events, inability to recruit sufficient number of subjects, etc.)?

Yes

Please explain

If a significant percentage of patients in the treatment group have unanticipated adverse events or any concern for their short/long term safety the project will be halted immediately. If it does not appear that we will be able to establish our numbers in 1 year, the project will be halted.

We anticipate being able to sign up 2 patients a week. If we are averaging less than 1 patient a week for a month we will stop the study. As this will likely be difficult to recover from.

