### A.8. Data analysis

#### A.8.1. Summarize the statistical analysis strategy for each specific aim.

Our primary goal is to test the difference between two independent groups at one week post op. Our feasible total sample size is 80 subjects. The progression of the ASEPSIS score over the six week post op recovery period will not be rectilinear. All patients are expected to be infection free with very low ASEPSIS scores immediately following the operation and are likely to be fully healed at six weeks. Attempting to model the timecourse of the ASEPSIS score with splines or multiple dummy variables and including all potential covariates would require considerable degrees of freedom and model tweaking based on intermediate assessments of model fit. Such a model would likely be too saturated to yield meaningfully narrow standard errors and holds considerable danger for overfitting. This modeling process does have some value for exploratory purposes, and we will employ it as such, but it will not be appropriate for confirmatory hypothesis testing. Instead, we note that the timepoint when differences in wound healing are most pronounced is after one week. Because subjects will be randomized to the two arms, we can consider the relevant population to be balanced on their covariates. The null hypothesis is simply that the treatments do not differ in ASEPSIS score at one week post op. Thus, we have a two independent groups t-test as a valid test

of our a-priori hypothesis.

A biostatistician ([name], NC TRACS) has been recruited and will provide the statistical computations and interpretive analyses required for the exploratory model-based analyses of the data. Estimates of effect magnitude, confidence intervals and sensitivity analyses will augment the exploratory modeling that will be conducted.

**A.8.2. What are the practical objectives of the study? Examples: pilot study to obtain data for a grant proposal, train junior investigators, create a registry, develop new assay methods, pilot-test procedures, evaluate feasibility, generate hypotheses, estimate parameters, test hypotheses.**

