**A.8.4. Provide a compelling justification for the proposed sample size in terms of the likelihood of achieving each aim.**

Over the course of the study period, there will be a finite number of possible enrolled subjects. We expect to enroll a total target sample size of  $N = 80$  eligible subjects. Our funding will provide for 40 patients to undergo the new treatment plan with 40 standard dressing subjects as a comparison. We anticipate that about 10 subjects will have incomplete data due to compliance, drop-out, and other causes. This will result in a recruitment of up to 90 subjects in order to result in 80 subjects completing the trial.

Our primary goal is to test the difference between two independent groups at a specific time point (namely, one week post op). We can think of this as a two independent groups t-test. With  $n_1=40$  vs  $n_2=40$ , we will have 80% power to reject the null if the difference between the means of the two conditions were 0.63 standard deviations apart (and with greater power if the differences were bigger). Any difference of less than 0.63 SDs would be seen as not clinically significant. Small differences in the score of 1-2 points would fall within this and can be attributed to observer differences and would likely not be sensitive for detecting any risk for surgical infection.

The experimental dressing is expected to have benefit by reducing wound healing characteristics related to complications (ASEPSIS score) and subsequently reducing postoperative infections. There is an extremely low rate of infections in primary total hip arthroplasty surgeries and infection cannot be measured with this limited population (0.5% to 3.0% of the population). Adverse secondary events also have a low incidence and our study is not designed or powered to identify a statistically significant difference in these events, although such events will be recorded and examined for exploratory purposes. The ASEPSIS score allows a lower sample size that is within our reach to detect changes and will be used to identify infection risk.

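### The plan gives no way to score the wound of a patient who is in hospital on postoperative day 7, so a few primary scores could go missing for reasons tied to the outcome

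*Combined protocol and SAP*

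**What the plan says.** Section A.8.1 fixes the primary comparison: "Our primary goal is to test the difference between two independent groups at one week post op". Section A.4.2 says where that score is taken: "The patients will return to clinic on Post op day seven". Section A.7.1 is looser on timing (patients "will return to clinic around post op day 7 and 14"), and no visit window in days is set.

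Three answers in B.3 put research contact in the outpatient setting:
- B.3.2: "Contact will be limited to outpatient clinic visits that will involve the recruitment and wound checks".
- B.3.5: "All subjects will be studied at the UNC Orthopaedic clinic".
- B.3.6: "All patient contact will occur in outpatient clinic rooms that will only contain the individual involved in the research study".

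The ASEPSIS table in A.1.1 has four items scored by percentage of wound affected, plus additional points for treatment, culture and length of stay, including "Hospitalization >14 days- 10". Table 1b schedules every item at week 1 and week 2 only. Aim 1 also names a 6-week score, but Table 1b has no 6-week column.

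On missing data, A.8.4 says: "We anticipate that about 10 subjects will have incomplete data due to compliance, drop-out, and other causes".

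**The concern.** The plan expects some patients to be back in hospital. A.7.1 keeps a list to catch readmissions, A.7.4 discusses hips that need surgical irrigation, and Aim 2 counts returns to the operating room. Taken as written, a patient in a hospital bed on day 7 has no clinic visit and therefore no standardised wound-area score for the primary analysis.

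Patients in hospital for a wound problem are plausibly those with high ASEPSIS values. Losing them lowers the observed mean of whichever arm has more of them. If that is the standard-dressing arm, the benefit of NPWT is understated. If it is the NPWT arm, the device is flattered. A.8.4 would count these patients among its roughly 10 incomplete cases, with nothing to separate them from ordinary attrition.

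**Working it through.** **1. The plan's own figure.** Inputs from A.8.4 are 40 per arm and a difference of 0.63 SD. Alpha is not stated, so two-sided 0.05 is assumed. Power is 80.4% by the normal approximation and 79.5% by the noncentral t, which agrees with the stated 80%. This point does not dispute that figure.

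**2. Is there an inpatient route?** Three other passages might supply one.
- A.4.3 keeps patients whose care departs from protocol under evaluation for the intention-to-treat analysis, but the evaluation it refers to is the clinic visit.
- A.8.5 allows recording at the point of care and review of medical records. Records can supply antibiotics, debridement, culture and stay. They cannot supply the wound-area items as judged by the two clinic examiners named in A.4.7.
- A.7.3 withdraws patients whose complications need more treatment. This conflicts with A.4.3 and could remove the same patients wherever they are.

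None of the three says how an inpatient's wound is scored.

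**3. How many points depend on examination?** Wound-area items: 5 + 5 + 10 + 10 = 30. Additional points: 10 + 5 + 10 + 10 + 10 = 45. The total is 75 if both debridement items may count. The 30 wound-area points are the part that records cannot replace.

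**4. Effect of omitting one patient (assumed scores).** Take an arm of 40 in which 39 patients average 2 and one scores S. The full mean is (39 × 2 + S)/40, and the mean without that patient is 2. The shift is therefore (S − 2)/40.
- S = 30: 28/40 = 0.70
- S = 40: 38/40 = 0.95 (for example pus 6, separation 4, antibiotics 10, operative debridement 10, culture 10)
- S = 50: 48/40 = 1.20

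For scale, A.8.4 attributes differences of 1-2 points to observers.

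**5. The shift against sampling error (assumed SD of 2 among the other 39).** With S = 40, the arm's variance is [38 × 4 + (39/40) × 38²]/39 = (152 + 1407.9)/39 = 40.0. The SD is then about 6.3 and the standard error of the arm mean is 6.3/√40 ≈ 1.0. The 0.95-point shift is just under one standard error.

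**6. Selection compared with simple loss of numbers.** Suppose one control patient lying d SD above the rest is lost, and the true difference is 0.63 SD. The visible difference becomes 0.63 − d/40. With d = 2 it is 0.58 SD (power about 72%), and with d = 4 it is 0.53 SD (about 64%). Losing one patient at random (39 vs 40) leaves power at 78.9%. The first two figures hold the SD fixed. Removing an extreme value also shrinks the SD, so they overstate the cost.

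**7. How many patients?** The 0.5% to 3% infection rate in A.1.1 and A.8.4 gives 40 × 0.005 = 0.2 to 40 × 0.03 = 1.2 infections per arm over all follow-up, and fewer by day 7. Inpatients for other reasons would add to this, but the document gives no rate.

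**8. The stay item.** On day 7 about 7 postoperative days have passed, so a stay over 14 days cannot have occurred and the 10 points are zero for everyone. On day 14 exactly 14 days have passed, so the item is still not met at an on-time visit. The week-1 range is therefore 75 − 10 = 65 points at most.

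**The case against.** The strongest reply is that B.3 does not set a scoring rule. B.3.2 answers a form question about contact duration and B.3.6 one about privacy. Read literally, they clash with research activity that the plan itself places in hospital: the team supplies the dressing during surgery, and the NPWT dressing is replaced on day 2. Nowhere does the document say that inpatients go unscored. This stands as a caution. The loss follows from what the text provides for and is not an announced exclusion. It does not close the gap, because A.4.2 independently ties the day-7 score to the clinic and no alternative is written down.

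A second reply is that the illustration uses an extreme patient, that such patients will be few, and that the shift sits within about one standard error of the arm mean. That also stands and limits the size of the point. It does not make the loss unrelated to outcome.

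A third reply is that A.7.3 is the more explicit threat, since it withdraws patients with complications wherever they are. This is correct, and it means that amending B.3 alone would not be enough.

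A reader might also infer three stronger things that the documents do not support:
- **That a patient in hospital on day 14 loses the primary score.** Only week 1 is primary. Someone scored on day 7 loses the week-2 score alone.
- **That the stay item can never score.** This is certain at week 1. At week 2 it holds only if the visit is on time, and A.7.1 allows approximate timing with no window.
- **That the unusable 10 points weaken the primary test.** An item that is zero for every patient in both arms changes no mean, SD or t statistic.

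**Conclusion.** The plan has a real but modest gap: no procedure yields the four wound-area items for a patient in hospital on day 7, and any resulting loss would probably be related to outcome. It rests on two inferences: that the clinic setting in A.4.2 and B.3 would be followed as written, and that day-7 inpatients include some with serious wound problems. If one such patient were lost from one arm, the bias would be about 0.7 to 1.2 points under the assumed scores. Similar losses in both arms would largely cancel in the difference. The expected number is small and cannot be estimated from the document. The mistimed stay item is a matter of scheduling and of the stated range, and has no bearing on the primary test.

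**What to change.** 1. Amend B.3, and A.4.2 to match, so that a patient in hospital on day 7 (primary) or day 14 (secondary) is scored at the bedside that day by the same two clinic examiners, with treatment and culture items taken from the chart. If the patient is at another hospital, complete those items from records and report the wound-area items as missing, with the reason.
2. Reconcile A.7.3 (withdrawal for complications) with A.4.3 (continued evaluation for intention-to-treat), so that scores from these patients are collected and kept in the analysis. This concerns data retention only and implies nothing about how the patients should be treated.
3. Move the item for a stay over 14 days out of the week-1 and week-2 columns of Table 1b, record it once at the existing 6-week visit, and state the week-1 range as 0-65.

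The cost is a few sentences, one moved case report form field and an occasional ward visit by staff already on the study. Patients make no extra visits.
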